7.7.1 Analyses of Clinical Safety Laboratory Results

All clinical laboratory evaluations including clinical chemistry, hematology, coagulation and urinalysis, and pregnancy tests will be performed per Protocol SoA.

For each test, baseline is defined as the last non-missing value prior to first dose of the study treatment.

All post-baseline summaries will include results collected on or after the date of the first dose of study intervention and within 30 days of last known dose of study intervention. Shifts from baseline to worst post-baseline CTCAE Version 5.0 or later grade (including unscheduled visits) will be presented by frequency and percentage for select laboratory parameters. For those parameters where worst is an increase or a decrease from baseline, separate summaries will be presented.

Time to onset of and duration of first post-baseline hematologic abnormalities of hemoglobin decreased, platelet count decreased and neutrophil count decrease will be summarized for each grade using descriptive statistics.

Listings of all subjects with clinically significant abnormal results including concurrent elevated ALT $\geq 3 \times$ upper limit of normal (ULN) or AST $\geq 3 \times$ ULN AND bilirubin $> 2 \times$ ULN or ALT $\geq 3 \times$ ULN and concurrent INR > 1.5 at any time post-baseline will be presented over time.

Listings of all laboratory values (hematology, chemistry, coagulation, urinalysis, pregnancy tests, and other screening test results) including results from unscheduled visits will be provided. The

listing will flag all out of normal ranges values and will include change from baseline for each post-baseline measurement (where applicable).

Adverse Events of Clinical Interest (ECI)

Adverse events of Clinical interest are defined based on sponsor pre-defined standardized MedDRA queries (SMQs) extracted using MedDRA preferred terms as listed in RMC-4630 Events of Clinical Interest document.

ECI will be summarized by category, subcategory, and preferred term. In addition, time to onset (days) of treatment-emergent ECI of any grade, grade ≥ 3 and their associated durations of resolved events will be summarized for treatment arm, each category and sub-category (where applicable) using descriptive statistics. Time to first occurrence of treatment-emergent ECI is calculated as time from first dose date of study treatment (RMC-4630 or sotorasib) – AE start date + 1. Duration of resolved adverse events is calculated as the AE end date – AE start date + 1.

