will be followed through the last study visit and be noted as “continuing” if not resolved at this visit. Any SAE that is determined to be study treatment related (possibly, probably, or definitely related) will be followed to resolution or stabilization, until it is determined to be irreversible by the investigator, the subject is lost to follow up, or it has been determined that the study treatment is not the cause of the AE/SAE. AE/SAE reporting will end after the subject initiates alternative cancer treatment. During the Extended-Use phase of the study, only SAEs (irrespective of causality) and related AEs will be reported in the EDC. All SAEs will also be reported on the SAE Report Form.

¹⁸ Record all concomitant medications including any prescription medications, over the counter preparations, and transfusions received by subject from 7 days preceding C1D1 through EOT. During the Extended-Use phase, concomitant medications given for SAEs only will be recorded.

¹⁹ Subjects should be instructed to bring their pills and diary to every clinic visit, or to submit diary information at that time.

²⁰ Hematology includes the following: RBC count, hemoglobin, hematocrit, MCV, MCH, % reticulocytes, platelet count, WBC count, and differential (neutrophils, bands [if available], lymphocytes, monocytes, eosinophils, basophils, other cells). NOTE: Testing must be performed and reviewed before dosing on C1D1. If hematology samples are obtained within the previous 72 hours as part of screening, then re-testing on C1D1 is not required. For subsequent visits after C1D1, samples may be obtained up to 72 hours prior to the visit. During the Extended-Use phase, hematology testing will be performed according to local standards of care.

²¹ Serum chemistry includes the following: sodium, potassium, chloride, bicarbonate/carbon dioxide, BUN, creatinine, glucose (non-fasting), albumin, total protein, calcium, magnesium, phosphorus, uric acid, lipase, GGT, ALT, AST, total and direct bilirubin, and ALP. NOTE: Perform tests and review results before dosing on C1D1. If chemistry samples were obtained within the previous 72 hours as part of screening, then re-testing on C1D1 is not required. Plasma is permitted. For subsequent visits after C1D1, samples may be obtained up to 72 hours prior to the visit. During the Extended-Use phase, serum chemistry testing will be performed according to local standards of care.

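### SAP 7.7.1 counts a pre-dose C1D1 laboratory sample as both baseline and post-baseline, which hides grade improvements and gives Day 1 onsets to pre-existing cytopenias in subjects who have such a sample

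*SAP*

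**What the plan says.** SAP 7.7.1 fixes baseline by order relative to dosing: "For each test, baseline is defined as the last non-missing value prior to first dose of the study treatment". It fixes the start of the post-baseline period by calendar date: "All post-baseline summaries will include results collected on or after the date of the first dose of study intervention". The second rule has no time-of-day condition.

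The Protocol's Schedule of Activities (Table 1) places the C1D1 samples before dosing. Footnote 20, on hematology, says "Testing must be performed and reviewed before dosing on C1D1". Footnote 21, on chemistry, says "Perform tests and review results before dosing on C1D1". Both footnotes also allow the C1D1 draw to be skipped: "If hematology samples are obtained within the previous 72 hours as part of screening, then re-testing on C1D1 is not required", and "If chemistry samples were obtained within the previous 72 hours as part of screening, then re-testing on C1D1 is not required".

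Two outputs in SAP 7.7.1 depend on these definitions. The first is the shift table from baseline grade to worst post-baseline CTCAE grade; SAP 6.1 says it uses every scheduled and unscheduled visit. The second is the cytopenia output: "Time to onset of and duration of first post-baseline hematologic abnormalities of hemoglobin decreased, platelet count decreased and neutrophil count decrease will be summarized". That sentence goes on to say the summary is made for each grade. It does not require the grade to be worse than at baseline. SAP 6.1 makes the date of first dose Day 1.

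**The concern.** One definition orders records by dose and the other by date, so they overlap on the day of first dose. A pre-dose C1D1 result is the baseline value and also falls inside the post-baseline window. No text in the SAP or Protocol removes it from the second set.

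Anemia and thrombocytopenia are two of the four potential risks of RMC-4630 listed in Protocol 2.1.1. Clinically significant laboratory changes are part of a secondary endpoint. Entry criteria admit hemoglobin from 9 g/dL, platelets from 100 × 10⁹/L and neutrophils from 1.5 × 10⁹/L, so some subjects may already have low counts when treatment starts. If those entry values count as post-baseline events, the onset and duration summaries mix entry status with on-treatment change. Whether a given subject is affected then depends on when the last pre-treatment sample was scheduled.

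**Working it through.** The documents state no figure on this point, so there is none to reproduce. The check applies the SAP's rules literally and compares the result with a window that opens strictly after the first dose.

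**1. Who is affected**

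| Last pre-dose sample | Baseline record? | In post-baseline window? |
|---|---|---|
| Drawn on the C1D1 date, before dosing | Yes | Yes, because it is dated on the day of first dose |
| Drawn on an earlier date within 72 hours, C1D1 draw skipped | Yes | No |

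**2. Shift table**

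Let b be the baseline grade (0 to 4) and m the worst grade strictly after first dose (0 to 4), giving 5 × 5 = 25 pairs. With a C1D1 sample, the literal worst post-baseline grade is max(b, m). With a strict window it is m.

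| Rule | Improved | Same | Worse |
|---|---|---|---|
| Literal SAP, max(b, m) | 0 | 15 | 10 |
| Strictly after dose, m | 10 | 5 | 10 |

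All 10 improving pairs move to no change, since max(b, m) is never below b. The 10 worsening pairs are the same under both rules. These are counts of possible pairs, not of expected subjects.

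**3. Onset of a cytopenia**

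Take a subject at Grade 1 on the pre-dose C1D1 sample, with later samples on Days 8, 15 and 22 (C1D8, C1D15 and C2D1). The first day at Grade 1 or above is:

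| Course | Literal SAP | Strictly after dose | Strictly after dose, and worse than baseline |
|---|---|---|---|
| Grade 1 persists | Day 1 | Day 8 | No onset |
| Grade 1, rising to Grade 2 on Day 15 | Day 1 | Day 8 | Day 15 |
| Grade 1, resolved by Day 8 | Day 1 | No onset | No onset |

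The move from Day 1 to Day 8 comes from the date rule. The move from Day 8 to no onset, or to Day 15, comes from the missing worsening requirement. These are two separate faults. In the second course, Grade 2 is first recorded on Day 15 under every rule, so the distortion falls on the grade present at entry.

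**4. How many subjects**

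SAP 2.3 gives a maximum of N = 46. The share q with a given count low at entry and the share c with a C1D1-dated draw are not in the documents, so both are assumptions. Taking them as independent, spurious Day 1 onsets = N × q × c:

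- q = 10%, c = 25%: 46 × 0.10 × 0.25 = 1.15, about 1
- q = 30%, c = 50%: 46 × 0.30 × 0.50 = 6.9, about 7
- q = 50%, c = 100%: 46 × 0.50 × 1.00 = 23
- c = 0: none

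**The case against.** The strongest defence is that the word post-baseline already implies a record other than the baseline one, and that the disputed sentence mainly sets the 30-day end of the window. SAP Section 1 also sends further variable definitions to a programming specification that is not among these documents and may drop the baseline record. This lowers the certainty that the double count would occur in practice. It does not repair the text: the SAP states a start date, a C1D1 pre-dose sample satisfies it, and a programmer following the SAP would include it. An unseen document cannot be assumed to override it.

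The defence is right on scope, and three stronger readings fail:

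- A reader might infer that no subject's shift can show improvement and that everyone low at entry gets a Day 1 onset. The 72-hour provision rules this out for subjects whose baseline sample carries an earlier date.
- A reader might infer that laboratory toxicity is miscounted in the shift tables. The worsening counts, which carry their safety message, do not change.
- A reader might infer that the onset and duration outputs describe entry status instead of drug effect. They are reported by grade, so grades first reached on treatment keep their correct onset.

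It is also fair that all analyses are descriptive. DLTs (Protocol 8.4) and the expansion stopping rule (SAP 7.7) rest on adverse events and not on these summaries. The laboratory listings show each value with its change from baseline, so a careful reader could spot the Day 1 records.

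**Conclusion.** The SAP is wrong as written, within limits. For subjects with a pre-dose sample dated C1D1, improvements in worst grade are shown as no change, and a hemoglobin, platelet or neutrophil decrease present at entry is given a Day 1 onset at that grade. The associated duration then also starts on Day 1. A second gap, the absence of a worsening requirement, would leave persistent pre-existing cytopenias with an onset at the next visit even with a corrected window.

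The size cannot be fixed from the documents. The range of about 1 to 23 of 46 subjects rests on the assumed 10–50% low at entry and 25–100% with a C1D1 draw. Local lower limits of normal, which decide who counts as low, are not given. The primary endpoint, the DLT assessment and the stopping rule are untouched. Correction is still worthwhile because two of the affected outputs concern named potential risks of RMC-4630.

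**What to change.** Amend SAP 7.7.1 in two places.

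1. Define post-baseline laboratory results as those collected after the first dose by date and time. Treat C1D1 samples without a collection time as pre-dose, and exclude the record used as baseline from every post-baseline summary.
2. Define onset of a hematologic abnormality as the first post-baseline CTCAE grade higher than the baseline grade, and duration as the time until return to the baseline grade or better.

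Both changes are needed, since the first alone moves a persistent pre-existing cytopenia from Day 1 to about Day 8. One consequence to accept knowingly is that a count which recovers and later falls back only to its entry grade will not be counted as an onset; it remains visible in the listings. The cost is two SAP sentences and a programming flag, with no new data collection. The programming specification should be checked for agreement.

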This statistical analysis plan (SAP) has been developed after review of the clinical study protocol RMC4630-03 (Original Protocol Version 1.0 dated 21 June 2021; Version 2.0 22 July 2021, Version 3.0 21 March 2022; Version 4.0 21 November 2022 and electronic case report form (eCRF).

This SAP describes the planned statistical methods for evaluating the efficacy, safety, tolerability, and PK of RMC-4630 in combination with sotorasib data for this study. Additional details of variable definitions are included in the supplemental Standard Programming Specification document. The planned table, figure, and listing (TFL) to be presented in the clinical study report (CSR) is provided in the accompanying TFL shells document.

This SAP supersedes any statistical considerations identified in the protocol; where considerations are substantially different, they will be so identified. If additional analyses are required to supplement the planned analyses described in this SAP, they may be performed and will be identified accordingly in the CSR.

This SAP is written with consideration of the recommendations outlined in the International Conference on Harmonization (ICH) E3 guideline Structure and Content of Clinical Study Reports, ICH E8 guideline General Considerations for Clinical Trials, and ICH E9 guideline Statistical Principles for Clinical Trials.

The document history is presented in [Appendix A](#).

2. Protocol Details

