6.1 Study Day and Visit Windows

Day 1 is defined as the date of first dose of study treatment. For days on or after the first dose of study treatment:

Study day = non-missing date of assessment/event - date of first treatment + 1

For days before the first dose of study treatment:

*Study day = non-missing date of assessment/event - date of first treatment
(one day prior to date of the first dose will be considered 'Day -1')*

For all analysis populations, all data will be analyzed using nominal scheduled study visits as defined in the SoA, i.e., scheduled visits. The only exception is for clinical safety laboratory evaluations, the analysis of shifts from baseline to worst post-baseline will use all scheduled and unscheduled visits within the study phase.

No visit windows will be applied for summary and analysis.

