7.7 Safety Analyses

Safety endpoints of the study are the incidence, nature, and severity of treatment-emergent adverse events (TEAEs), SAEs, clinical laboratory tests, vital signs, and ECGs.

Adverse events (AEs) will be collected from the date that informed consent was signed. Verbatim terms for each AE will be coded using MedDRA Version 25.0 or later and graded per the NCI CTCAE Version 5.0 or later. Treatment-emergent adverse event (TEAE) is defined as those AEs with an onset on or after the date of the first dose of study intervention and within 30 days of last known dose of study intervention. Treatment-related AEs are treatment-emergent AEs reported as related to RMC-4630 or sotorasib.

All AE summaries will be presented for the initial combination dose level and overall using the treated population.

Safety Stopping Rules

During dose expansion after the final expansion dose has been selected, evaluation of all Grade 4 or higher treatment-related adverse event rates will be conducted to assess if the unacceptable toxicity threshold has been reached. If this threshold is met, enrollment to dose expansion will be halted pending review of safety data. After reviewing the totality of data from both CodeBreaK 101C and cumulative data from this study, one of the following actions may be taken:

1. Terminate the study
2. Amend the protocol to potentially improve the benefit/risk for subjects (e.g., increase safety monitoring, modify dose/schedule, mandate premedication)
3. Continue dose expansion without any changes

The stopping rules use a Bayesian approach to pause the enrollment if the posterior probability is $\geq 80\%$ that the Grade 4 or higher treatment-related adverse event rate is greater than 20%. The stopping boundaries shown in Table 1 assume a prior distribution of Beta (0.4, 1.6). The operating characteristics with the pre-specified batch size of 10 new subjects are summarized in Table 2.

Table 1: Stopping Boundary by Number of Subjects

Number of Subjects Treated	Number if Subjects with Grade 4 or Higher Treatment Related Adverse Events to Halt Enrollment
10	≥ 4
20	≥ 6
30	≥ 9
40	Expansion Complete

Table 2: Operating Characteristics of Stopping Rules

True Grade 4 or Higher Treatment-Related Adverse Event Rate	Probability of Early Stopping of Dose Expansion	Average Dose Expansion Sample Size
0.1	2.1%	39
0.15	9.7%	38
0.2	25.8%	34
0.25	47.7%	29
0.3	69.2%	23

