- Summary of TEAEs leading to dose modification of sotorasib by PT
- Summary of TEAEs leading to dose modification of sotorasib by SOC and PT
- Summary of TEAEs leading to dose modification of RMC-4630 or sotorasib by PT
- Summary of TEAEs leading to death by SOC and PT
- Summary of ECI by category, sub-category, and PT
- Summary of time to onset of ECI by category and sub-category

Treatment-related AEs include those events considered by the investigator to be possibly, probably, or definitely related to study drug (RMC-4630 or sotorasib). AEs with missing relationship status will be classified as related.

If the same PT is reported multiple times for a subject within the same SOC, that PT will only be reported once within that SOC. As with the PT, if a subject has multiple reported events within the same SOC, that SOC will only be reported once. If a subject experiences the same AE with more than one severity, or with more than one relationship to study intervention, the most severe rating or the stronger causal relationship to study drug(s) will be assigned to the event. Any missing severity or outcome will not be imputed and classed as unknown/missing.

Subject listings of all reported AEs, SAEs, AEs leading to dose reduction, treatment interruption, treatment discontinuation from the study, and death will be provided. The listings will be sorted by subject ID, study day, SOC/PT/verbatim term, and severity grade.

Deaths

Summary listing of reported death by any cause will be provided. The number and percentage of subjects experiencing deaths (all-cause) and causes of deaths will be summarized, and will also be categorized as death within or beyond 30 days of last dose of study drugs which occurs later.

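### The SAP's time-to-onset formula for events of clinical interest subtracts the dates in the wrong order, and its named liver criteria leave out AST with INR >1.5

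*SAP*

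**What the plan says.** **ECI onset.** The ECI paragraph of SAP 7.7.1 defines time to first occurrence as "time from first dose date of study treatment (RMC-4630 or sotorasib) – AE start date + 1". The next sentence reads "Duration of resolved adverse events is calculated as the AE end date – AE start date + 1". The general rule for days on or after first dose, in SAP 6.1, is "Study day = non-missing date of assessment/event - date of first treatment + 1". SAP 7.7 defines treatment-emergent AEs as "those AEs with an onset on or after the date of the first dose of study intervention", with an upper limit of 30 days after the last dose. The onset variable is to be summarised descriptively for any-grade and grade ≥3 ECIs, and SAP 7.7.3 lists the table "Summary of time to onset of ECI by category and sub-category".

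**Liver listing.** SAP 7.7.1 plans "Listings of all subjects with clinically significant abnormal results including concurrent elevated ALT" ≥3×ULN or AST ≥3×ULN together with bilirubin >2×ULN, or ALT ≥3×ULN together with INR >1.5. AST is named in the bilirubin arm but not in the INR arm. The Protocol pairs INR >1.5 with AST or ALT in four places: Section 8.4 (at ≥3×ULN), and Table 6, Section 6.7.6 and Table A2-1 footnote 1 (each at >3×ULN).

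**The concern.** The onset formula is a calculation rule that gives the wrong answer if it is followed. It runs opposite to the SAP's own study-day convention and, because of the treatment-emergent definition, can never return more than 1. Programmed literally, every onset after Day 1 in the planned ECI table would be zero or negative. If it is programmed correctly, the program departs from the SAP text, and SAP Section 9 asks for deviations to be described and justified in the study report.

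The liver point is smaller. Raised AST with INR >1.5, without raised ALT or bilirubin, meets the laboratory part of what the Protocol treats as possible severe drug-induced liver injury. That finding is a DLT under Section 8.4 and a reason to stop both drugs permanently under Table 6. The listing that spells out liver criteria does not name it.

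**Working it through.** **1. Is the dash a minus sign?** The onset expression ends in + 1. The duration formula in the next sentence has the same layout and can only be a subtraction (end date minus start date plus 1). So the dash is a minus, and the two dates are in the wrong order.

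**2. Size of the onset error.** Put first dose on Study Day 1 and onset on Study Day d, with d ≥ 1 from the treatment-emergent definition.

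- SAP 6.1: d − 1 + 1 = d
- SAP 7.7.1 as printed: 1 − d + 1 = 2 − d
- Error: d − (2 − d) = 2(d − 1) days

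| Onset (Study Day) | SAP 6.1 | SAP 7.7.1 as printed | Error (days) |
|---|---|---|---|
| 1 | 1 | 1 | 0 |
| 2 | 2 | 0 | 2 |
| 8 | 8 | −6 | 14 |
| 15 | 15 | −13 | 28 |
| 43 | 43 | −41 | 84 |

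**3. Effect on the summary statistics.** Each value x becomes 2 − x. The mean and median therefore become 2 minus the true value, the minimum and maximum swap roles, and the SD does not change. As an illustration with assumed onsets (not trial data) on Days 2, 8, 15, 29 and 64:

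- Correct: mean 118/5 = 23.6, median 15, range 2 to 64, SD 24.7
- As printed (0, −6, −13, −27, −62): mean −108/5 = −21.6, median −13, range −62 to 0, SD 24.7

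**4. Liver criteria.** Treat raised ALT, raised AST, raised bilirubin and INR >1.5 as four yes/no flags, which gives 16 combinations.

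- Protocol laboratory rule, (ALT or AST) and (bilirubin or INR): 3 × 3 = 9 combinations qualify.
- SAP named criteria, ((ALT or AST) and bilirubin) or (ALT and INR): the bilirubin arm gives 3 × 2 = 6. The INR arm adds 2 more (ALT yes, bilirubin no, INR yes, AST either way), making 8.
- The one left out is ALT no, AST yes, bilirubin no, INR yes.

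The SAP sentence carries no brackets, so the and/or terms could be grouped in other ways. There are 14 possible groupings, and none of them captures this combination. The count identifies the missing pattern; it says nothing about how often it would occur, and the documents give no frequency.

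**5. When scheduled tests could show the pattern.** Protocol 6.7.6 schedules liver tests after C1D1 at C1D8, C1D15, C2D1, C2D15 and C3D1, then Day 1 of each later cycle and EOT. Table 1 footnote 22 schedules INR at screening, C1D1, C3D1, every other later cycle and EOT. Of the five liver-test visits from C1D8 to C3D1, only C3D1 has a scheduled INR. C3D1 is nominally 2 × 21 + 1 = Day 43. Before then, unless EOT comes first, the pattern can arise only from unscheduled INR tests.

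**The case against.** On ECI onset, the other side would call this a transposed subtraction with no rival analysis behind it. The wording around the formula shows the intent, SAP 6.1 gives the right rule, and negative onset times would expose themselves at first sight, so a biased result is unlikely to reach a report unnoticed. The SAP also says "Additional details of variable definitions are included in the supplemental Standard Programming Specification document". That specification is not among these documents and may be correct. All of this stands and limits the likely harm. It does not make the printed formula correct.

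On the liver listing, the objections have more weight:

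- The criteria follow the word including, so a clinically significant AST-with-INR case can still be listed.
- All laboratory values, unscheduled ones included, are listed with out-of-range flags.
- Table A2-1 footnote 1 requires events with these abnormalities to be reported as SAEs, and SAE listings are planned.
- The key components for detecting Hy's Law cases in Protocol Appendix 2 name bilirubin and not INR, so the Protocol is not fully uniform.
- The Protocol rule also requires the absence of cholestasis and other causes, which neither the SAP criteria nor the corrected wording below tries to encode.
- Section 6.7.6 gives INR as an example test when liver injury is evaluated, so unscheduled INR results may matter more than the visit schedule suggests.

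These points show that no subject's data would be lost. What remains is that four places in the Protocol give the INR alternative for AST or ALT, and a listing that names its criteria drops AST from one arm without a stated reason.

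**Conclusion.** Both points hold, and both are minor. The ECI onset formula is wrong as written: it returns 2 − d for an onset on Study Day d, an error of 2(d − 1) days, and is right only for Day 1. This is a finding about the SAP text. Whether any output would be wrong depends on the programming specification, which cannot be checked here. The liver criteria leave one of nine qualifying laboratory combinations unnamed, and the effect is confined to one targeted listing. SAE and DLT capture do not depend on that listing. Neither point touches ORR, the sample size, dose escalation or the safety stopping rule.

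**What to change.** Two one-line edits to SAP 7.7.1:

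- ECI time to onset: `AE start date − first dose date + 1`, as in SAP 6.1. Check that the programming specification says the same.
- Liver listing: `(ALT or AST ≥3×ULN) and (bilirubin >2×ULN or INR >1.5)`. The ≥3×ULN cut-off matches Protocol 8.4 and also takes in every case meeting the >3×ULN wording used elsewhere in the Protocol. With the brackets, the listing names all nine combinations and no others.

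The cost is the SAP text change and a check of the specification. No new data are needed.
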